#### 1. Study design and specific aims

Predicting and Addressing Colonoscopy Non-adherence in Community Settings (PRECISE) is an individualrandomized clinical trial of a patient navigation intervention versus usual care to improve participation in followup colonoscopy in a federally qualified health center. The study consists of two phases: **Phase I** (Aim 1) is a milestone-driven planning phase to externally validate the risk-prediction score, stratify patients' probability of adhering to follow-up colonoscopy, and adapt patient navigation materials for the local context. **Phase II** (Aims 2–3) is a large-scale, targeted patient-randomized controlled trial that will include ~1200 patients across ~32 clinics in western Washington State.

The study has the following aims:

**Aim 1:** Validate externally the predictive risk score using Sea Mar Community Health Center's robust data including 29,000 patients age-eligible for colorectal cancer screening; stratify patients according to risk of non-adherence to follow-up colonoscopy; and adapt patient navigation program for the local context.

Aim 2: Assess the effectiveness, costs, and cost-effectiveness of a centralized, phone-based patient navigation program for follow-up colonoscopy receipt for patients at moderate risk or high risk for non-adherence. (See Handling of Deviations and Protocol Amendments 9.1 and 9.2)

**Aim 3:** Assess differences in the intervention arms in secondary outcomes (e.g. time to colonoscopy receipt, noshow/canceled appointments, colonoscopy quality) and moderators of intervention effectiveness (e.g. probability level, intervention dose, and patient age, ethnicity, and sex) (See **Handling of Deviations and Protocol Amendments 9.3**)

## 2. Patient Identification

Clinic staff will prospectively identify patients ages 50 to 75 with an abnormal fecal test (FIT) result. A preadjudication process will be completed to confirm eligibility for all patients by the patient navigator and a clinical team (including the study gastroenterologist).

Patients will be excluded if they have had a recent negative colonoscopy (within the past 3 years) or have a limited set of health conditions (e.g. metastatic cancer, on hospice or in a nursing home, end-stage renal disease, home oxygen use).

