For all aspects of the study, we will only be including patients aged 50-76 with a positive FIT test. Some exclusions may apply based on appropriateness of screening (i.e. if they had prior colorectal cancer, or are on hospice or dialysis).

This intervention is part of clinical care. Subjects may refuse colonoscopy as part of clinical care, but will have opportunity to opt out of the study.

c. Vulnerable Populations

This study will not include children or neonates by design (aged 50-76). Prisoners were not knowingly included in the cohort. Pregnant women were not targeted but may have been included incidentally. Decisionally impaired adults will not be excluded as CRC screening is recommended for these patients.

d. Setting

The proposed project is a partnership with Sea Mar Community Health Centers. Sea Mar operates 34 medical clinics (28 clinics will participate in this trial; non-participating clinics are specialty sites) and serves a patient population of ~250,000; ~29,000 are eligible for CRC screening. The proportion of Latino patients is 37%. Clinic personnel are sensitive to, and reflective of, the diverse populations they serve. Sea Mar has a fully integrated EHR platform tailored for primary care (Allscripts, Chicago, Illinois). Sea Mar has participated in efforts to raise its CRC screening rates by using a direct-mail FIT approach followed by automated and live reminders.

All analysis will be conducted at KPNW. SeaMar (#FWA00000701) and Portland State University (#FWA00003920) will cede IRB oversight to the KPNW IRB (FWA 00002344).

e. Recruitment Methods/Data Collection

Retrospective Risk Model

For the retrospective risk model, patients who are aged 50-75, and have had an abnormal FIT test will be identified for the last 5 years. The risk model will identify clinical, lab, encounter, and demographic characteristics to predict those unlikely to undergo colonoscopy. The analysis of the abnormal FIT patients over the past 5 years may include more than 6,000 patients.

Patient Navigation

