We will conduct a large-scale, targeted, patient-randomized controlled trial that will include ~1200 patients at 28 Sea Mar clinics. Patients will have to be 50-75 years old, and have an abnormal fecal test (FIT). We will compare rates of follow-up colonoscopy completion in ~1200 patients having either a moderate or low risk of colonoscopy adherence who are randomized to receive either a telephone-based (including text messages for scheduling, reminders, and outreach for "difficult to reach" patients) program of patient navigation delivered by trained clinical staff or usual care. Patients will be randomized based on county of their assigned clinic. Patients will be randomized using a stratified approach that considers county. The randomization will result in 600 patients assigned to the patient navigation arm and 600 assigned to the usual care arm.

All navigation and usual care will be conducted by the clinical teams at SeaMar (nurses, MA's, providers, etc.). The patient navigator will undergo intensive training during the startup phase of the study. The navigator will receive coaching (quality assurance supervision) by KPCHR study staff. Coaching will include routine (daily/weekly) check-in phone calls, and listening in on patient navigation calls and tracking navigation fidelity. KPCHR staff will continue to monitor patient navigation calls throughout the trial as part of the intervention fidelity assessment. The patient navigator will help patients address and resolve barriers to follow-up care, such as, transportation barriers through ride-share services or medical transport services.

We will assess rates of colonoscopy receipt by probability group. At the end of the evaluation, if the intervention is found to be successful, it will be offered to all patients in the usual care and surveillance arms who did not get a follow-up colonoscopy.

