| Eligibility criteria: FIT positive plus referred | Eligibility criteria: FIT positive and referred and reviewed by clinic champion/GI (to reduce post-randomization drop out, randomized in error) |
| Final outcome determination: Medical record review | Final outcome determination: Medical record review plus records request to GI and blinded adjudication |
| Cost analysis, timeline w/o pandemic interruptions | Eliminate the cost-analysis activities to extend our recruitment interval to get closer to reaching our 1200-patient goal |

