#### 6. Statistical Methods

#### 6.1. Primary outcome analysis

Primary analysis will rely on a modified intention-to-treat (ITT) that excludes patients from both arms who are randomized in error (determined to be ineligible based on information in the medical record that was missed during the eligibility determination process). Patients in the primary ITT data analysis will retain their randomization assignment irrespective of whether they received patient navigation. Two secondary per-protocol analyses are planned: one that excludes patients who were determined ineligible because they moved, or clinical reasons that occurred post-randomization; and a second that additionally excludes patients who were never reached by the navigator.

Sea Mar's EHR data will be transferred to CHR every 6 months via a secure file transfer. We will examine the distribution of all variables prior to analyses and verify all missing and out-of-range values. We will assess the ICC. If the ICC is .001 or above, we will use hierarchical generalized linear modeling to account for clustering of patients within clinics. If the ICC is less than .001, we will use adjusted logistic regression without accounting for clustering to optimize parsimony. Because the primary outcome is binary (i.e., follow-up colonoscopy, yes/no), we will use a model with a logit link and binomial distribution (i.e., multilevel logistic regression). The independent variable will be arm (dummy-coded) with usual care as the reference group. 'Clinic' will be modeled as a random effect. The model will include county as a covariate (fixed effect) as it was a stratification factor for randomization.

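### The primary analysis removes patients as randomized in error under two different definitions, with no stated blinding of that decision and no all-randomized result to check it

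*SAP*

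**What the plan says.** **Who is counted.** SAP 6.1 describes a modified intention-to-treat analysis that "excludes patients from both arms who are randomized in error". Table 1 builds the same removal into the denominator of the primary outcome and of time to colonoscopy.

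**What the term means.** SAP 6.1 defines it as ineligibility resting on medical-record information that the eligibility check overlooked. SAP 6.2 defines it as ineligibility resting on a health condition that was present before randomization. SAP 6.2 expects some such patients despite the chart review before randomization.

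**Eligibility.** SAP 2 says "Patients will be excluded if they have had a recent negative colonoscopy (within the past 3 years) or have a limited set of health conditions" and then gives examples: metastatic cancer, hospice or nursing home, end-stage renal disease and home oxygen. Protocol 5b says that some exclusions may apply, naming patients "if they had prior colorectal cancer, or are on hospice or dialysis". On age, Protocol 5b says "we will only be including patients aged 50-76 with a positive FIT test" and 5c repeats that range. The trial paragraph in Protocol 5e says "Patients will have to be 50-75 years old, and have an abnormal fecal test (FIT"), and SAP 2 and 8.1 also give 50 to 75.

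**Blinding.** SAP 3 states that neither the research team nor clinic staff are blinded. SAP 5.1 describes an arm-blinded abstractor for the colonoscopy outcome.

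**Other analysis sets.** Two per-protocol analyses are planned. The first also removes patients who moved or became unsuitable for clinical reasons after randomization. The second further removes patients whom the navigator never contacted. The added sensitivity analyses (SAP 8.7) concern time windows and quarterly counts.

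**The concern.** Removing ineligible patients after randomization is harmless only if the decision does not depend on arm or outcome. That requires a fixed rule, facts that existed before randomization, and a decision-maker who knows neither arm nor outcome. Here the rule is worded in two ways, its list is open, and no blinding is stated for the decision.

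Contact also differs by arm. Navigated patients are offered a six-topic call protocol, so pre-existing conditions have more chances to surface. SAP 5.1 recognises the same mechanism for the outcome, expecting fuller capture of colonoscopies in navigated patients, and answers it with blinded abstraction. Eligibility removals get no matching protection.

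Patients removed for ineligibility will mostly be people who did not have a colonoscopy. If more of them leave one arm, that arm's completion rate rises without any effect of treatment. Because every planned analysis set starts after the removals, the results would not show it.

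**Working it through.** **1. The two definitions side by side.**
- A recent negative colonoscopy, or an age outside the range, that was overlooked in the record meets SAP 6.1. Neither is a health condition, so SAP 6.2 does not clearly cover it.
- A pre-existing condition that was not in the record and emerges later, in a navigator call or at the gastroenterology visit, meets SAP 6.2. It does not clearly meet 6.1, which concerns recorded information that was missed.
- SAP 6.2 assigns referrals cancelled after the pre-procedure visit and history review to the first per-protocol exclusion. If the cause was a long-standing condition, the same patient could also be read as randomized in error, and so leave the primary analysis.

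**2. The exclusion lists.** Hospice is in both, and dialysis overlaps with end-stage renal disease. Prior colorectal cancer as such is named only in the Protocol. The 3-year colonoscopy rule, metastatic cancer, nursing home and home oxygen are named only in the SAP. Neither list is closed.

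**3. Size of the group.** The documents give no expected number, so there is no plan figure to reproduce. All removal shares below are assumptions. From the documents: 600 per arm (SAP 3) and 44% completion under usual care (SAP 4). The 50% navigation rate is assumed.

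**4. Formula.** With true completion p, share removed e, and completion c among those removed, the rate after removal is (p − e·c)/(1 − e). If all removed patients are non-completers (c = 0), this is p/(1 − e).

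| Removed, navigation / usual care | Patients of 600 | Calculation | Difference |
|---|---|---|---|
| 0% / 0% | 0 / 0 | 0.50 − 0.44 | 6.0 points |
| 5% / 5% | 30 / 30 | 0.50/0.95 − 0.44/0.95 = 0.5263 − 0.4632 | 6.3 points |
| 3% / 1% | 18 / 6 | 0.50/0.97 − 0.44/0.99 = 0.5155 − 0.4444 | 7.1 points |
| 5% / 2% | 30 / 12 | 0.50/0.95 − 0.44/0.98 = 0.5263 − 0.4490 | 7.7 points |
| 2% / 5% (reverse) | 12 / 30 | 0.50/0.98 − 0.44/0.95 = 0.5102 − 0.4632 | 4.7 points |

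The choice c = 0 is the extreme. With c = 0.22 in both arms, the 5% / 2% case is (0.50 − 0.011)/0.95 − (0.44 − 0.0044)/0.98 = 0.5147 − 0.4445, or 7.0 points.

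**5. No true effect** (44% in both arms, c = 0, no clustering). The spurious difference is d = 0.44/(1 − e₁) − 0.44/(1 − e₂). The two-sided rejection rate is Φ(d/SE − 1.96) + Φ(−d/SE − 1.96), with SE from the two remaining samples.
- 2% / 0%: d = 0.9 points, rejection about 6%.
- 5% / 2%: d = 0.4632 − 0.4490 = 1.4 points; SE = √(0.4632·0.5368/570 + 0.4490·0.5510/588) = 0.0293; rejection about 8%.
- 5% / 0%: d = 2.3 points, rejection about 12.5%.
- 5% / 5%: d = 0, rejection 5%.

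**6. Equal removal costs little power.** For 44% versus 53.2%, the pair in SAP 4 without design effect, power is Φ[(0.092√n − 1.96·√(2·0.486·0.514))/√(0.44·0.56 + 0.532·0.468)]. This gives 89% at n = 600 per arm, 88% at 570 (5% removed) and 81% at 480 (20% removed). SAP 4 states 80% for this difference, so its figure does not reproduce at 600 per arm. It errs on the cautious side and is a separate matter. The issue here is bias, not power.

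**The case against.** The plan has real safeguards:
- Eligibility is confirmed before randomization by the navigator and a clinical team that includes the gastroenterologist (SAP 2). The Protocol's modifications table adds this review in order to reduce such errors, so numbers may be small.
- Removal applies to both arms.
- Both definitions point towards facts that preceded randomization.
- Patients who moved or became unsuitable later stay in the primary analysis, which closes much of the route by which a navigator's conversations could remove non-completers.

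All of this stands and limits the likely size. It does not settle who decides, with what knowledge, or under which of the two wordings.

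Three stronger readings are tempting, and the documents do not support them.
- *The Protocol and SAP set different age limits for the trial.* They do not. The 50–76 wording is in Protocol 5b and 5c. The trial paragraph in 5e agrees with the SAP on 50–75. This is an inconsistency inside the Protocol and could concern only patients aged 76.
- *Certain patients are kept under one document and removed under the other.* Neither text says so. One list is optional and the other gives examples, so they are open and different rather than flatly contradictory. The referral condition ("FIT positive and referred and reviewed by clinic champion/GI") is in the modifications table, and the SAP takes referral for granted elsewhere, so little rests on it.
- *Removal is unequal, or favours navigation.* Nothing in the documents shows this. The direction is also uncertain. Records are requested after one year for patients without evidence of a colonoscopy. If those records were also used to judge eligibility, which the SAP does not say, ineligibility could surface more often in the arm with more non-completers.

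A mismatch between lists is in itself neutral between arms. The 7.1 and 7.7 points measure unequal ascertainment, which a closed list alone would not prevent.

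**Conclusion.** The point holds as a weakness in how the primary analysis set is defined. Membership depends on a decision made after randomization that has two definitions, an open list and no stated blinding, and no planned analysis includes everyone randomized. The differing eligibility texts taken alone are a documentation matter.

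The size is unknown. Under the assumed shares, unequal removal moves a 6.0-point difference to 7.1 or 7.7 points, or down to 4.7 if the imbalance runs the other way. Equal 5% removal gives 6.3. With no true effect, a 5% versus 2% imbalance raises the two-sided error rate from 5% to about 8%. These figures assume that all removed patients are non-completers and, for the error rate, no clustering. They show what could pass unseen, not what is expected.

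**What to change.** 1. Use one definition of randomized in error in SAP 6.1 and 6.2, resting only on chart facts dated before randomization. State how it is separated from the clinical reasons that trigger the first per-protocol exclusion.
2. Have the decision made blind to arm and outcome. The existing blinded abstractor can do this from a record extract that ends at the randomization date, before looking at the outcome. If that person has already seen outcomes, another arm-blinded reader is needed.
3. Report the number removed and the reasons, by arm.
4. Report the all-randomized result beside the modified intention-to-treat result, using the same model.
5. Reconcile the eligibility passages: age in Protocol 5b and 5c against 5e and the SAP, and the exclusion lists in Protocol 5b and SAP 2. The sponsor decides which text applies.

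SAP 8.7 describes recruitment and evaluation through December 2022 in the past tense, so item 5 cannot change who was enrolled. Items 2 to 4 remain possible from existing records. The list should not be re-decided with outcomes in view.

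The cost is a few sentences in each document, a modest amount of extra chart review and analysis, and one more row in the results table.

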## 3. Randomization and blinding

Patients meeting clinical eligibility criteria will be randomized by the health center (Sea Mar) analyst to receive either the patient navigation intervention or usual care. Study identification numbers linked to patients will be uploaded into REDCap® on a weekly basis, for patients in the navigation arm, with date of abnormal FIT result. We anticipate that the time between patient identification and study randomization will take about 2 weeks. (See **Handling of Deviations and Protocol Amendments 9.4**)

Randomization will be performed using a stratified approach that considers patients' county of residence. We will use Sealed Envelope (London, UK) to randomize patients 1:1 to navigation or usual care in blocks of 4 to 8 individuals, stratified on county of residence. For practical reasons, neither the research team nor the clinic staff will be blinded to randomization assignment. However, measures have been taken to preserve as much blinding as possible. Staff trained in navigation will not perform colonoscopy referral coordination (as part of usual care). Patients randomized to patient navigation are removed from the referral coordinator list to eliminate potential outreach by referral coordinators. In this way, the patient navigation intervention will not be overlaid on usual care, as doing so would result in multiple contacts from multiple clinic staff. (Consistent with usual care, referral

coordinators will contact referred patients who have not completed a colonoscopy making up to three phone attempts; patients who are not reached will be sent a letter.)

The randomization will result in 600 patients assigned to the patient navigation arm and 600 assigned to the usual care arm. We will assess rates of colonoscopy receipt at 1 year overall, and will perform a heterogeneity of treatment effect analysis to assess differential effects by age, sex, ethnicity, language preference, insurance status, and probability of adherence (based on the risk model), using data from the electronic health record.

CHR analysts will assign a colonoscopy completion probability, based on the risk prediction model. These methods have been described previously.

#### 4. Sample size and power

Estimates of the ICC at the clinic level for CRC screening collected from several different studies range from .001 to .10, with the majority ranging from .02 to .05. The ICC for our prior CRC screening study in similar clinics (STOP CRC) was .03. Though we anticipate a lower ICC for this study given that we will partner with a single large federally qualified health center (FQHC) with more uniform procedures and practices (i.e., less betweenclinic variability) rather than eight smaller FQHCs in the STOP CRC trial, we will use an ICC estimate of .03 as a conservative upper estimate. Given that larger ICCs increase the design effect and reduce the power of the test, we will provide the minimum detectable odds ratios for the primary outcome for both a near zero ICC and an ICC of .03; we will base our analyses on an average cluster size of 42 patients per clinic (1200 abnormal FIT patients/32 clinics). Based on data from prior studies, we expect that 9% of patients will have a positive FIT, and 44% of patients under usual care will complete a follow-up colonoscopy within 1 year (based on chart abstracted data from 08/05/2017 to 08/04/2018 (N = 715 charts)). In a logistic regression framework, we will have 80% power to detect a difference of 12.9% (completion rate in intervention of 56.9%, OR=1.68) when accounting for the design effect and a difference of 9.2% (completion rate in intervention of 53.2%, OR=1.45), assuming no design effect at a two-tailed alpha level of .05. We believe a difference between 9.2% and 12.9% is both achievable and clinically significant. Notably, our minimal detectable difference is 2-3 times lower that the effect size reported in the New Hampshire Colorectal Cancer Screening Program (27 percentage points).

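### SAP section 4: the detectable differences of 9.2 and 12.9 points do not follow from the stated inputs, and 12.9 uses a clinic-randomised inflation in a patient-randomised trial

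*SAP*

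**What the plan says.** SAP section 4 takes 44% completion under usual care, 80% power and a two-sided alpha of .05, and reports two minimum detectable differences.

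- With near-zero clustering: "a difference of 9.2% (completion rate in intervention of 53.2%, OR=1.45), assuming no design effect at a two-tailed alpha level of .05".
- With clustering: "80% power to detect a difference of 12.9% (completion rate in intervention of 56.9%, OR=1.68) when accounting for the design effect".

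The clustering inputs are "we will use an ICC estimate of .03 as a conservative upper estimate" and an "average cluster size of 42 patients per clinic (1200 abnormal FIT patients/32 clinics". SAP section 3 gives the sample size, "The randomization will result in 600 patients assigned to the patient navigation arm and 600 assigned to the usual care arm", and the design, which is to "randomize patients 1:1 to navigation or usual care in blocks of 4 to 8 individuals, stratified on county of residence". The Protocol (sections 2, 4, 5.d and 5.e) has 28 participating clinics; SAP section 1 has about 32.

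Two interpretive sentences rest on the figures: "We believe a difference between 9.2% and 12.9% is both achievable and clinically significant", and "our minimal detectable difference is 2-3 times lower that the effect size reported" in the New Hampshire programme, which was 27 percentage points.

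**The concern.** For 600 per arm and a 44% control rate, 9.2 points is too large a detectable difference when no design effect is applied. The cluster size disagrees with the division printed beside it. The second figure also relies on an inflation factor meant for a different design.

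Section 4 is the SAP's only statement of the effect the primary comparison can detect. As written, a reader cannot tell which N, cluster size or formula produced it, and the sentences on clinical significance and on the comparison with New Hampshire inherit the problem.

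**Working it through.** **Inputs.** p0 = .44, power 80%, two-sided alpha .05, ICC .03 and cluster size m = 42 (SAP section 4); 600 per arm (SAP section 3); 28 clinics (Protocol). Normal quantiles are 1.960 and 0.842.

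**Formula.** n per arm = [1.960 × √(2p̄(1−p̄)) + 0.842 × √(p0(1−p0) + p1(1−p1))]² / (p1−p0)², where p̄ is the mean of p0 and p1. For a design effect D = 1 + (m−1) × ICC, replace n by n/D.

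**1. The stated rates and odds ratios agree with each other.** (.532/.468)/(.44/.56) = 1.447 and (.569/.431)/(.44/.56) = 1.680. A slip in a single printed number is therefore unlikely.

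**2. No design effect.** For p1 = .532 the squared bracket is (1.385 + 0.592)² ≈ 3.911, and 3.911/.092² = 462 per arm, or 924 in total. Solving instead for p1 at 600 per arm gives .5207, a difference of 8.07 points with OR 1.383 (check: 3.911/.0807² ≈ 600). Other standard versions give nearly the same: 8.07 (arcsine), 8.09 (Wald on the log-odds) and 8.24 (continuity-corrected). Power at 600 per arm is 89% for 9.2 points.

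| Total analysed | Detectable difference (points) |
|---|---|
| 1200 | 8.07 |
| 1100 | 8.43 |
| 1000 | 8.84 |
| 960 | 9.03 |
| 924 | 9.20 |

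**3. With the SAP's own design effect.** At m = 42, D = 1 + 41 × .03 = 2.23 and 600/2.23 = 269 effective patients per arm. That gives 12.05 points (OR 1.62), and 85% power for 12.9. At m = 37.5, D = 2.095 and the value is 11.68; at m = 42.9, D = 2.256 and the value is 12.12.

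**4. Can one N give both figures?** Not at m = 42. The 12.9 figure needs 3.904/.129² = 234.6 effective patients per arm, 469 in total. Multiplied by 2.23 this is 1046 patients, where the value without a design effect is 8.65. Conversely, 924 patients with D = 2.23 give 13.7. The stated pair implies D = 924/469 = 1.97, hence m = 1 + .97/.03 ≈ 33. The pair in SAP section 6.3 implies much the same ratio: (ln 2.98/ln 2.17)² = 1.99. A set that reproduces both section 4 figures is 924 patients in 28 clinics (m = 33, D = 1.96), giving 9.20 and 12.87. That equals 1200 patients in 28 clinics less 23%. It is inference: the documents state neither the 924 nor the 23%.

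**5. Cluster size.** 1200/32 = 37.5. The stated 42 lies close to 1200/28 = 42.9, so the clinic count may have been updated and the cluster size left alone.

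**6. Is D the right factor?** The formula 1 + (m−1) × ICC applies when all patients in a clinic are allocated to the same arm. Here individuals are randomised 1:1 within county, so each clinic is expected to contribute to both arms and its shared effect largely drops out of the contrast. If randomisation were balanced within clinics the factor would be 1 − ICC = .97, giving 8.0 points.

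A simulation used 1200 patients, blocks of 4 to 8 in 8 counties, unequal clinics, an ICC of .03 and an unadjusted test, with 2000 to 2500 trials per cell. For 28 and 32 clinics respectively:

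- power was .82 and .81 at 8.07 points;
- power was .90 and .89 at 9.2 points;
- power was above .99 at 12.9 points in both;
- type I error was .053 in both.

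Clustering can still cost power if the treatment effect itself varies between clinics. Adding SD²/K to the unpooled variance of the difference (K clinics; 8.05 points with no variation) gives the following. The SDs are assumptions; the documents give none.

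| SD of effect between clinics | K = 32 | K = 28 |
|---|---|---|
| 5 points | 8.43 | 8.48 |
| 10 points | 9.45 | 9.63 |
| SD needed to reach 12.9 | 20.4 | 19.1 |

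**The case against.** The strongest reply is that section 4 offers an openly conservative bracket. It reports both a near-zero ICC and an ICC of .03, says a lower ICC is expected, and SAP section 6.1 plans a clinic random effect, so some allowance for clustering is reasonable. That explains the choice of ICC. It does not justify the clinic-randomised formula: a random clinic intercept does not create that inflation when patients are randomised individually. Variation of the effect between clinics would, but the SAP assumes none.

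A second reply is that the figures may be carried over from another design rather than miscalculated. The Protocol Modifications table records that the highest-probability quintile was once not to be randomised. If 80% of 1200 was used (an assumption), 960 patients in 28 clinics give 9.03 and 12.75, near both stated values but not equal to them. This is a fair caution against treating 924 as a diagnosis. It still leaves section 4 out of step with its own inputs.

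Third, the practical consequence is small. This stands. The errors are conservative, and the recruitment and evaluation intervals in SAP section 8.7 run only to December 2022. The value 8.1 is also a best case, because SAP section 6.1 excludes patients randomised in error and the Protocol Modifications table treats 1200 as a goal. At 960 to 1000 analysed the value is 8.8 to 9.0, close to 9.2. The clinic-count difference may be a later update, and the New Hampshire comparison is correct for the stated figures (27/9.2 = 2.9; 27/12.9 = 2.1).

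**Conclusion.** The concern holds, as a minor point. At 1200 analysed the value without a design effect is about 8.1 points (OR 1.38), against 9.2 (OR 1.45) as stated. The stated clustering inputs give 12.05 points, against 12.9. No single N yields both figures at a cluster size of 42, and 42 is not 1200/32. These results rest only on the SAP's own inputs and are not sensitive to the choice of standard formula.

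Separately, the full clinic design effect is not the right allowance for individual randomisation within county. Justifying 12.9 through varying effects would need a between-clinic SD of about 19 to 20 points. The trial is not underpowered by these errors: on the stated inputs it can detect smaller differences than the SAP claims. How far that holds in practice depends on the number analysed.

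**What to change.** Issue a clarifying note to SAP section 4 that does the following.

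- State the N, number of clinics, cluster size, any loss allowance and the formula.
- Restate the value without a design effect as about 8.1 points (OR about 1.38) at 1200 analysed, with values for fewer patients (8.8 at 1000, 9.0 at 960).
- Remove 12.9 and OR 1.68, or replace them with an explicit allowance for treatment effects that vary between clinics, stating the assumed SD.
- Reconcile 28 with about 32 clinics, and the cluster size with whichever count is kept.
- Update the sentence on clinical significance and the New Hampshire comparison to match (27/8.07 = 3.3).
- In section 6.3, drop or justify the design-effect interaction odds ratio (2.98 or 0.34) on the same ground, and state the stratum sizes behind 2.17 and 0.46. The latter pair is not shown to be wrong.

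The cost is SAP wording only, with no change to conduct or to the planned analysis.
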